12.3	Abbreviations	62
12.3.1	Summary of Figures	64
12.4	Protocol Amendment History	65
13	REFERENCES.....	66

STATEMENT OF COMPLIANCE

The trial will be conducted in accordance with Good Clinical Practice (GCP), applicable United States (US) Code of Federal Regulations (CFR), state laws and local requirements. The Principal Investigator will assure that no deviation from, or changes to the protocol will take place without prior agreement from the Investigational New Drug (IND) or Investigational Device Exemption (IDE) sponsor, funding agency and documented approval from the Institutional Review Board (IRB), except where necessary to eliminate an immediate hazard(s) to the trial participants. All personnel involved in the conduct of this study have completed Human Subjects Protection and GCP Training.

The protocol, informed consent form(s), recruitment materials, and all participant materials will be submitted to the IRB for review and approval. Approval of both the protocol and the consent form must be obtained before any participant is enrolled. Any amendment to the protocol will require review and approval by the IRB before the changes are implemented to the study. All changes to the consent form will be IRB approved; a determination will be made regarding whether a new consent needs to be obtained from participants who provided consent, using a previously approved consent form.

1 PROTOCOL SUMMARY

1.1 Synopsis

Title: A Phase 2, Historically Controlled Study Testing the Efficacy of TTFIELDS (Optune[®]) with Adjuvant Temozolomide in High-risk WHO Grade II and III Astrocytomas (FORWARD)

Study Description: Phase 2, multi-institutional, open-label historically controlled study. The hypothesis of this study is that the addition of TTFIELDS treatment to adjuvant temozolomide (TMZ) will significantly increase overall survival (OS) in patients with newly diagnosed Grade II and III astrocytoma with Telomerase Reverse Transcriptase (TERT) promoter mutations only compared to historical controls.

Objectives: Primary Objective:

1. To determine whether TTFIELDS combined with adjuvant temozolomide increases OS in patients with newly diagnosed Grade II and III astrocytoma with TERT promoter mutation only, compared to historical (dating back to 2016) and contemporaneous controls at the same project sites.

Secondary Objectives:

1. To determine whether the combination of TTFIELDS and adjuvant temozolomide is safe in the newly diagnosed high-risk Grade II and III astrocytoma.

2. To determine whether TTFields combined with adjuvant temozolomide increases progression-free survival (PFS) in patients with newly diagnosed Grade II and III astrocytoma with TERT promoter mutation only, as compared to historical (dating back to 2016) and contemporaneous controls at the same project sites.

3. To evaluate quality of life (QOL) using Karnofsky Performance Status (KPS), Mini-Mental Status Examination (MMSE), and European Organization for Research and Treatment of Cancer Quality of Life Questionnaire - Cancer and Brain (EORTC QLQ-C30/BN20) scale in patients treated with TTFields combined with adjuvant temozolomide, compared to historical (dating back to 2016) and contemporaneous controls at the same project sites.

Exploratory Objectives:

1. To determine whether the addition of TTFields to adjuvant temozolomide significantly increases mutation burden, as compared to historical (dating back to 2016) and contemporaneous controls in samples from the same project sites.

2. To determine whether TTFields increases immune cell infiltration.

3. To determine whether TTFields induces immunogenic cell death in tumor.

Endpoints: Primary Endpoint: Overall survival (OS)

Secondary Endpoints: Progression free survival (PFS), safety and quality of life

Study Population: Patients with tissue-based diagnosis of high-risk Grade II or III astrocytomas, 18 years or older, of both genders after surgery or biopsy followed by radiation therapy with concurrent temozolomide.

Phase: 2

Description of Sites/Facilities Enrolling Participants: This study is being conducted in a consortium of 10-20 high volume brain tumor centers in the U.S.

Description of Study Intervention: Treatment with TTFields (Optune®) with Adjuvant Temozolomide: TT Fields are applied through surface transducer arrays placed directly on the shaved head. Temozolomide is available in either tablet or IV infusion.

Study Duration: 60 months: 36 months enrollment plus 24 months follow-up/study completion

Accrual Goal: 100 interventional subjects and up to 100 historical and contemporaneous control subjects

Participant Duration: 24 months (study treatment) plus follow-up until death or until the study is complete/terminates.

1.2 Schema

[figure not shown]

Figure 1. This is a phase 2, Single Arm, Historically Controlled Study of the Combination of Adjuvant Temozolomide plus TTFields in Patients with Newly Diagnosed Grade 2 and 3 Glioma with TERT Promoter Mutation Only. The interventional arm will combine TTFields with adjuvant TMZ after the completion of definitive chemoradiotherapy. Study treatment may continue past first tumor recurrence. The primary endpoint will be overall survival. TMZ = Temozolomide; RT = Radiation Therapy.

1.3 Schedule of Activities (SoA)

TABLE 1: SCHEDULE OF ACTIVITIES: INTERVENTIONAL SUBJECTS

Study Procedure:	Screening ≤14 days prior to Day 0	Day 0 : Begin TMZ Treatment	Week 4 (-3/+7 days) and every 4 weeks until treatment stop	Week 8 (±7 days) and every 8 weeks only until treatment stop	Progression	After Treatment Stop (Week 4 (+/- 7 days) from end of treatment)	Survival follow-up
Informed Consent	X						
Medical History, Demographics	X						
Medication History	X						
MGMT methylation status	X						
Tumor Tissue Sample ⁹	X				X		
MRI of the brain ¹	X			X	X		
Physical Exam	X		X		X	X	
Neurological status, KPS	X		X		X	X	
CBC w/diff	X ¹⁰		X		X	X	
Pregnancy test (urine or serum)	X ¹⁰						
Biochemistry Panel ⁶	X ¹⁰		X		X	X	
Record Steroid Dose	X		X		X		
Quality of Life Questionnaires ²	X			X	X		
RANO	X			X	X		
Temozolomide Cycle		X ⁷	X ⁸				

Study Procedure:	Screening ≤14 days prior to Day 0	Day 0 : Begin TMZ Treatment	Week 4 (-3/+7 days) and every 4 weeks until treatment stop	Week 8 (±7 days) and every 8 weeks only until treatment stop	Progression	After Treatment Stop (Week 4 (+/- 7 days) from end of treatment)	Survival follow-up
Optune Therapy ⁴		X	X		X		
Optune Compliance ⁴			X				
Adverse Events		X	X	X	X	X	
Concomitant Medications		X	X	X	X	X	
Telephone Interview							X ⁵
DICOM Images shipped for electric fields mapping ¹¹		X			X		X

1) Screening MRI should be done within 21 days of study treatment start. MRI of the brain will be performed routinely at baseline and again every 8 weeks +/- 7 days until treatment termination or second progression, whichever is first. An MRI of the head will be obtained within 21 days in the event of clinical signs of progression. After the post-treatment follow up visit and the patient has not progressed by treatment termination, patient will have contrast-enhanced brain MRI every 3 +/- 1 months for 12 months, then every 6 +/- 2 months for 24 months, then yearly +/- 1 month thereafter or until disease progression, whichever comes first. All MRI scans should be performed with and without contrast and include the scalp.
							

2) Quality of Life will be measured using the EORTC QLQ-C30/BN20 and MMSE every 8 weeks +/- 7 days for the first 2 years then every 3 months thereafter.
							

3) Screening visit should occur within 14 days of adjuvant temozolomide start, with the exception of MRI which can be within 21 days (3 weeks) of adjuvant temozolomide start.
							

4) Optune therapy should start within two weeks of start of adjuvant temozolomide, but not more than 7 weeks from the end of temozolomide/RT and will be continuous throughout study. Compliance documentation will be obtained every 4 weeks +/- 7 days.
							

5) Every 3 months until death. The only data required during survival follow-up is DOD.
							

6) Biochemistry panel will include electrolytes, creatinine, bilirubin, liver enzymes.
							

7) Patients will begin treatment with temozolomide at 4 weeks (+14 days) from end of radiotherapy. Cycle 1 will be dosed at 150mg/m² daily for 5 consecutive days of a 28-day cycle.
							

Study Procedure:	Screening ≤14 days prior to Day 0	Day 0 : Begin TMZ Treatment	Week 4 (-3/+7 days) and every 4 weeks until treatment stop	Week 8 (±7 days) and every 8 weeks only until treatment stop	Progression	After Treatment Stop (Week 4 (+/- 7 days) from end of treatment)	Survival follow-up

8) Patients will begin treatment with temozolomide Cycle 2 and subsequent cycles every 4 weeks (-3/+7 days) at 200mg/m² PO daily for 5 consecutive days, if CTC hematologic toxicity for cycle 1 is grade < 1 and the CTC non-hematologic toxicity for cycle 1 is grade ≤ 2. If dose escalation is not appropriate, the dose should remain at 150 mg/m² PO daily for 5 consecutive days for Cycle 2 and onward.
							

9) Verification of tissue availability and location should be determined at screening visit. When available, formalin fixed and paraffin embedded (FFPE), pathology slides and/or frozen samples will be obtained for primary tumors and first recurrent tumors.
							

10) Labs to be completed within 3 days for pre-TMZ cycles. Screening and other labs are within the visit windows noted. Pregnancy Test required for WOCBP only at Screening.
							

11) DICOM images will be shipped to Beth Israel Deaconess Medical Center for electric field mapping analysis at baseline, first progression and second progression. Imaging performed between shipping time points should be included in the next shipment.
							

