4.3 Justification for Dose

4.3.1 Temozolomide

Dosing instructions are consistent with the usage guidelines for refractory anaplastic astrocytoma listed in the package insert. See package insert for full details.

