6.1.2 Dosing and Administration

6.1.2.1 Adjuvant Temozolomide Treatment

All patients will receive adjuvant temozolomide.

6.1.2.2 Adjuvant Phase Cycle 1:

Four to six weeks after completing the temozolomide + RT phase, the temozolomide is administered for an additional 12 cycles of adjuvant treatment. Dosage in Cycle 1 (adjuvant) is 150 mg/m² once daily for 5 days followed by 23 days without treatment.

6.1.2.3 Adjuvant Cycles 2-12:

At the start of Cycle 2, the dose is escalated to 200 mg/m², if the CTC non-hematologic toxicity for Cycle 1 is Grade ≤2 (except for alopecia, nausea and vomiting), absolute neutrophil count (ANC) is ≥ 1.5 x 10⁹/L, and the platelet count is ≥ 100 x 10⁹/L.

The dose remains at 200 mg/m² per day for the first 5 days of each subsequent cycle unless toxicity occurs. If the dose was not escalated at Cycle 2, escalation should not be done in subsequent cycles.

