6.1.2.4 Temozolomide Dose Reduction or Discontinuation

Dose reductions during the adjuvant phase should be applied according to Tables 7 and 8 below. Cycle 1 Day 1 should not start until the ANC is above 1.5 x 10⁹/L (1,500/μL) and the platelet count exceeds 100 x 10⁹/L (100,000/μL). If unable to start within the Cycle 1 start window, the patient will be considered a screen fail.

The next cycle of temozolomide should not be started until the ANC and platelet count exceed these levels. Dose reductions during the next cycle should be based on the lowest blood counts and worst non-hematologic toxicity during the previous cycle. Dose reductions or discontinuations during the adjuvant phase should be applied according to Tables 7 and 8. Routine blood monitoring should be conducted in accordance with local site procedures.

TABLE 7. TEMOZOLOMIDE DOSE LEVELS FOR ADJUVANT TREATMENT

Dose Level	Dose (mg/m ² /day)	Remarks
-1	100	Reduction for prior toxicity
0	150	Dose during Cycle 1
1	200	Dose during Cycles 2-12 in absence of toxicity

TABLE 8. TEMOZOLOMIDE DOSE REDUCTION OR DISCONTINUATION DURING ADJUVANT TREATMENT

Toxicity	Reduce temozolomide by 1 Dose Level ^a	Discontinue temozolomide
Absolute Neutrophil Count	<1.0 x 10 ⁹ /L	See footnote b
Platelet Count	<50 x 10 ⁹ /L	See footnote b
CTC Non-hematological Toxicity (except for alopecia, nausea, vomiting)	CTC Grade 3	See footnote b

^a: temozolomide dose levels are listed in table 7.

^b: temozolomide is to be discontinued if dose reduction to <100 mg/m² is required or if the same Grade 3 non-hematological toxicity (except for alopecia, nausea, vomiting) recurs after dose reduction.

CTC = Common Toxicity Criteria.

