6.2.2 Formulation, Appearance, Packaging, and Labeling

The complete package insert for temozolomide will accompany this protocol in lieu of an Investigator's Brochure.

The complete Optune Instructions for Use and Device Manual will accompany this protocol in lieu of a Device Manual.

Additionally, the Optune DSS may provide the patient with Optune Patient Information and Operation Manual, Optune Travel Support Brochure, Optune Patient Scalp Care Guidelines, etc. These are educational resources published by Novocure to better assist patients in understanding and using the device.

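### Table 1 footnote 8 states a temozolomide dosing rule for Cycle 2 onward that conflicts with sections 6.1.2.3 and 8.1.2 on escalation and with Table 8 on dose reduction

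*Combined protocol and SAP*

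**What the plan says.** **Footnote 8 (section 1.3, Table 1).** Cycle 2 and later cycles are given at 200 mg/m² "if CTC hematologic toxicity for cycle 1 is grade < 1 and the CTC non-hematologic toxicity for cycle 1 is grade ≤ 2". No toxicity is exempt. If escalation is not appropriate, the dose stays at 150 mg/m² "PO daily for 5 consecutive days for Cycle 2 and onward".

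**Sections 6.1.2.3 and 8.1.2.** These agree with each other. Escalation to 200 mg/m² needs Cycle 1 non-hematologic toxicity of grade 2 or lower, with the carve-out "except for alopecia, nausea and vomiting), absolute neutrophil count (ANC) is" at least 1.5 x 10⁹/L, and platelets of at least 100 x 10⁹/L. Both add: "If the dose was not escalated at Cycle 2, escalation should not be done in subsequent cycles".

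**Section 6.1.2.4, Tables 7 and 8.** The next cycle's dose depends on the lowest counts and worst non-hematologic toxicity of the cycle before. The dose falls one level for ANC below 1.0 x 10⁹/L, platelets below 50 x 10⁹/L, or grade 3 toxicity in the row "CTC Non-hematological Toxicity (except for alopecia, nausea, vomiting"). Table 7 places 150 mg/m² at level 0 and 100 mg/m² at level -1. Footnote b to Table 8 repeats the exemption for discontinuation: "if the same Grade 3 non-hematological toxicity (except for alopecia, nausea, vomiting) recurs after dose reduction".

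**Package insert.** Section 4.3.1 says "Dosing instructions are consistent with the usage guidelines for refractory anaplastic astrocytoma listed in the package insert", and section 6.2.2 says "The complete package insert for temozolomide will accompany this protocol".

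**The concern.** A chemotherapy dosing rule should give one dose for one patient. Here two current texts give different doses, and the protocol does not say which prevails. The escalation decision is taken once, at Cycle 2, so whichever text a site follows fixes that patient's ceiling for the rest of adjuvant treatment.

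Section 11.1.10 treats any noncompliance with protocol requirements as a deviation, reportable within 14 days. For a patient on whom the texts disagree, either dose breaches one of them. The synopsis plans 10-20 centers, so two sites, or a site and its monitor, could classify the same act in opposite ways.

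**Working it through.** The plan gives no figure to reproduce here. The check is to apply each text to the same patient.

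**Escalation at Cycle 2**

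| Condition | Footnote 8 | 6.1.2.3 and 8.1.2 |
|---|---|---|
| Non-hematologic limit | grade ≤ 2 | grade ≤ 2 |
| Exempt toxicities | none | alopecia, nausea, vomiting |
| Hematologic limit | CTC grade < 1 | ANC ≥ 1.5 and platelets ≥ 100 x 10⁹/L |

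Test patient A has grade 3 nausea or vomiting in Cycle 1, normal counts, and no other toxicity.

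- Footnote 8: the hematologic condition is met (grade 0). The non-hematologic condition fails (3 > 2). Dose: 150 mg/m².
- 6.1.2.3 and 8.1.2: the event is exempt and both counts pass. Dose: 200 mg/m².

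Reading the footnote's hematologic limit as a misprint for grade ≤ 1 changes nothing, because patient A fails on the non-hematologic condition.

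**Size for patient A**

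- Per day: 200 - 150 = 50 mg/m².
- Per 5-day cycle: 5 x 200 - 5 x 150 = 1,000 - 750 = 250 mg/m².
- After n cycles without later reductions: [750 + 1,000(n - 1)] - 750n = 250(n - 1) mg/m².
- At the planned minimum, n = 6: 250 x 5 = 1,250 mg/m².
- At the planned maximum, n = 12: 250 x 11 = 2,750 mg/m².

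The last figure is an upper bound for one patient. Later reductions, or stopping temozolomide at radiological progression, make the gap smaller.

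**Reduction at Cycle 2**

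Test patient B has a lowest Cycle 1 ANC below 1.0 x 10⁹/L and recovers enough to start Cycle 2.

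- Footnote 8, last sentence: escalation is not appropriate, so the dose remains 150 mg/m².
- Table 8 with Table 7: one level down from 150 mg/m² is 100 mg/m².

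The gap is again 50 mg/m²/day (5 x 150 - 5 x 100 = 250 mg/m² per cycle), but here the footnote gives the higher dose. The same follows for platelets below 50 x 10⁹/L or non-exempt grade 3 toxicity.

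**Which text is the outlier**

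Sections 6.1.2.3 and 8.1.2 and Table 8 all carry the exemption for alopecia, nausea and vomiting. Only footnote 8 lacks it.

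**The case against.** The strongest reply is that the footnote belongs to a schedule in the Protocol Summary, while the titled dosing section gives a clear rule that the visit procedures repeat. Its closing condition, that escalation be appropriate, could be read as shorthand for criteria set out elsewhere, with Table 8 still applying on top. It is true that the body text is consistent and shows what was intended. But the footnote is a complete instruction, with dose, days, criteria and consequence. It neither refers to section 6 nor yields to it.

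A second reply is that the package insert governs. The protocol cites the insert as consistent with its dosing and supplies it to sites, but does not say that it overrides the protocol's own criteria. Table 7 does not settle the matter either: it ties 200 mg/m² to absence of toxicity without giving a grade.

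A third reply is that the consequence is unproven. This stands. Section 2.1.3.1.2 lists nausea and vomiting among events seen in more than 30% of patients but gives no grades, so the number with grade 3 events in Cycle 1 is unknown. How often sites would dose from the footnote is also unknown.

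A reader might infer more on the hematologic side: that lymphopenia, or counts slightly low but above the ANC and platelet thresholds, would also divide the two rules. The documents do not reproduce the CTC hematologic grade limits, so this overlap cannot be shown from them.

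**Conclusion.** This is an internal inconsistency in an operative dosing rule, and footnote 8 is wrong as written. Two cases are established: grade 3 nausea or vomiting with normal counts (150 v 200 mg/m²), and Cycle 1 toxicity that meets a Table 8 reduction criterion (150 v 100 mg/m²). Each is a difference of 50 mg/m²/day for the patient concerned. The footnote is the stricter text on escalation and the more lenient one on reduction, so it cannot be defended as uniformly cautious. The conclusion rests on reading each text literally and on the absence of any stated precedence.

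It should not be read as a threat to the primary result. The cumulative amounts are bounds for one patient, not a trial-level effect. The planned OS comparison is an intent-to-treat log-rank test (Table 2, section 10.2.1) with no temozolomide dose term. Power, alpha and the SAE boundaries do not depend on the footnote.

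**What to change.** Replace the whole dosing rule in footnote 8, meaning both the escalation criteria and the sentence holding the dose at 150 mg/m², with a cross-reference to 6.1.2.3 and 6.1.2.4 (Tables 7 and 8).

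If the sponsor wants the rule visible in the table, copy the 6.1.2.3 criteria exactly, including the three exempt toxicities and the ANC and platelet thresholds, and qualify the last sentence so that it applies unless Table 8 requires a dose reduction. Correcting the escalation criteria alone would leave the conflict with Table 8 in place.

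The cost is a wording change to one footnote. Sections 6.1.2.3, 6.1.2.4 and 8.1.2 stay as they are, and design, sample size and analysis do not change.

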2 INTRODUCTION

2.1 Study Rationale

2.1.1 High-risk Grade II and III Gliomas

A long-standing observation in neuro-oncology concerns a group of Grade II and III gliomas that appear relatively indolent histologically but are highly aggressive and resistant to standard chemoradiation therapy with an overall survival rate similar to that of Grade IV astrocytomas (glioblastoma - GBM). Recent therapeutic advancements in low-risk Grade II and III gliomas have further shined the spotlight on this high-risk group, widely recognized as a major remaining roadblock to achieving long-term survival in all Grade II and III gliomas. In recent years, molecular and genomic reclassification of gliomas has identified this high-risk group of Grade II and III tumors that require special attention as new treatment modalities are developed in the hope of improving its outcomes. Addressing this unmet need is the overarching goal of this protocol.

Common point mutations at the R132 position of the cytosolic NADP+-dependent isocitrate dehydrogenase gene 1 (IDH1) occur in a majority of Grade II and III gliomas (70-80% in oligodendrogliomas and 60-70% in astrocytomas) and secondary GBM (~10%) [1-3] and confer better prognosis and response to therapy. At this position, the R132H mutation accounts for approximately 90% of all IDH1 mutations [1, 3]. Mutations in the related mitochondrial IDH gene IDH2 are much less common and exclusive of IDH1 mutations and occur at the position R172 with the R172K mutation accounting for nearly 65% of all IDH2 mutations [1].

Another important recurrent mutation that occurs exclusively in Grade II and III oligodendrogliomas is the 1p/19q co-deletion [per the new WHO grading system for brain tumors-[4]], which carries both positive prognostic and predictive values [5-7]. By this new classification, astrocytomas lack 1p/19q co-deletion and fare much worse compared to oligodendrogliomas, especially those without IDH mutations. New efforts have been directed at further defining these high-risk subgroups of astrocytomas, including ATRX mutations in alpha-thalassemia/mental retardation syndrome X-linked (ATRX) gene [8-10], which impair non-homologous end joining (NHEJ) repair and are correlated with the alternative lengthening of telomeres (ALT) phenotype, but are mutually exclusive with 1p/19q co-deletion (therefore, for the purpose of this study, the presence of ATRX mutations is considered equivalent to the absence of 1p/19q co-deletion) leading to improved response to cytotoxic treatment, and more recently mutations in the promoter of telomerase reverse transcriptase (TERT), the catalytic subunit of the enzyme telomerase, which, together with the telomerase RNA component (TERC), comprises the most important unit of the telomerase complex. TERT promoter mutation increase telomerase activity and occur in both astrocytomas and oligodendrogliomas of all grades [11, 12].

Until recently, treatment standards for WHO Grade II and III gliomas were poorly defined as few phase 3 clinical trials were available to delineate a role for adjuvant therapy after radiotherapy (RT), which historically had demonstrated a PFS, but not OS, benefit in several studies [13, 14]. In the last five years, however, three large phase 3 studies (two for Grade III and one for Grade II) have established an important role for adjuvant chemotherapy for the standard treatment for these tumors [15-17].

Similar to Grade II oligodendrogliomas, the addition of the chemotherapy regimen PCV to RT in Grade II astrocytomas increased both PFS and OS (Fig. 2A and 2C), although the magnitude of benefit in astrocytomas is significantly less compared to the more favorable oligodendroglioma subtype. As projected, the presence of IDH1 R132H mutation predicted for better response to PCV (Fig. 2B and 2D). However, since there was no breakdown in the fraction of IDH1 R132H mutation in astrocytomas and oligodendrogliomas in this study because the number of tumors lacking a IDH mutation was too few to assess the association with treatment [11], the assumption is that the predictive value of the IDH1 R132H mutation is of equal importance in both of these histologic subtypes. In addition, it is unclear, whether other mutations at positions R132 of IDH1 and R172 of IDH2 carry similar predictive value.

Grade II Astrocytomas

[figure not shown]

Figure 2. Role of IDH1 R132H Mutation in Grade II Astrocytoma. (A-B) PFS comparison of RT alone (RT) or RT + PCV in Grade II astrocytoma (A) and in all Grade II gliomas (both oligodendrogliomas and astrocytomas) (B) with IDH1 R132H mutation. (C-D) OS comparison of RT alone (RT) or RT + PCV in Grade II astrocytoma (C) and in all Grade II gliomas (both oligodendrogliomas and astrocytomas) (D) with IDH1 R132H mutation. (Adapted from Buckner JC et al. *N Engl J Med* 2016;374:1344-1355).

Of note, information on 1p/19q co-deletions was not available in this study; however, it can be assumed that there would be a strong correlation between the presence of 1p/19q co-deletions and better response to PCV and prognosis compared to those without 1p/19q codeletions, as demonstrated for Grade III gliomas. In summary, Grade II tumors without 1p/19q co-deletions (i.e. astrocytomas per new classification scheme [4]) and IDH mutations fare much worse compared to their counterparts with either or both of these recurrent alterations.

In Grade III gliomas, the predictive roles of 1p/19q co-deletions and IDH mutations, specifically the IDH1 R132H mutation, are better defined thanks to two large phase 3 studies [16, 17]. The presence of 1p/19q co-deletions (i.e. oligodendrogliomas per new classification [4]) significantly increased response to PCV chemotherapy and prolonged survival compared to 1p/19q intact tumors (i.e. astrocytomas) (Fig. 3). The additive presence of the IDH1 R132H mutation further defined 3 distinct groups of tumors with the combined 1p/19q co-deletions and IDH mutations group faring the best, the double negative the worst, and the single positive group in the intermediate (Fig. 4).

Grade III Gliomas

[figure not shown]

Figure 3. Role of 1p, 19q Codeletions in Grade III Glioma. OS comparison of RT alone (RT) or RT + PCV in Grade III gliomas with 1p, 19q codeletions (A) or without 1p, 19q codeletions (B). (Adapted from Gregory Cairncross et al. JCO 2013; 31:337-343).

Grade III Gliomas

[figure not shown]

Figure 4. Role of 1p, 19q Codeletions and IDH1 R132H mutations in Grade III Glioma. Kaplan-Meier estimates of OS for patients with a Grade III glioma (orange) or without 1p, 19q codeletions and with (blue) or without IDH1 R132H mutation after PCV + RT (A) or RT Alone (B). (Adapted from Gregory Cairncross et al. JCO 2013;31:337-343).

[figure not shown]

Figure 5. TERT Promoter Mutation only is associated with the worst prognosis in Grade II and III Glioma. The presence of IDH mutations and/or 1p/19q codeletions were able to rescue the poor prognosis associated with TERT promoter mutation. Triple-positive: IDH mutations, 1p/19q codeletions, and TERT promoter mutation; Triple-negative: No IDH mutations, 1p/19q intact, and no TERT promoter mutations. (Adapted from Eckel-Passow JE et al. *N Engl J Med* 2015;372:2499-2508).

2.1.1.1 Reclassification of WHO grade II and III astrocytomas with high-risk molecular features to molecular GBM

To further delineate and stratify risks within the double negative group of astrocytomas that are resistant to current standard chemoradiation therapy and whose survival approaches that of GBM, Eckel-Passow et al. scored 1087 gliomas, of which 596 were Grade II and III tumors, as negative or positive for the three biomarkers: 1p/19q co-deletions, IDH mutations, and TERT promoter mutations [11]. Using 11,590 controls, association between these genotypic groups and clinical data were examined. As previously demonstrated, TERT promoter mutation occurred in both the most aggressive form of gliomas (GBM) and the best prognostic group (oligodendrogliomas with 1p/19q codeletions and an IDH mutation) (Fig. 5). Importantly, astrocytomas that lacked the 1p/19q co-deletions and IDH mutations, and possessed TERT promoter mutation, exhibited the worst overall survival rate that was not dissimilar to that of GBM, suggesting that these tumors represent a molecular continuum with GBM even though histologically they are Grade II or III.

Beside the Eckel-Passow report [18], a large growing body of literature over the past decade confirms this distinct group of diffuse astrocytomas WHO grade II and III carrying the same molecular high risk features as primary astrocytomas WHO grade IV (i.e. GBM), despite their histologic appearance similar to regular WHO grade II and III tumors. This high-risk group of astrocytomas invariably carry isolated TERT promoter mutations without the presence of IDH mutations [19]. Recently the c-IMPACT-NOW consortium reaffirmed the central role of the poor prognostic indication of diffuse astrocytomas with TERT promoter mutations in the absence of IDH mutations [20], while others support the reclassification of this high-risk diffuse astrocytomas to represent molecular GBM [21], with an aggressive clinical course essentially similar to histologic primary GBM, and treated as regular GBM [3, 18,

21-24]. Although PCV has demonstrated efficacy in combination with radiotherapy in both grade II and III diffuse gliomas, including both regular-risk and high-risk astrocytomas [15-17], TMZ is increasingly being used in place of PCV because of 1) TMZ's proven activity against newly diagnosed GBM [25] and newly diagnosed grade III astrocytomas [26]; 2) TMZ given sequentially before or after RT resulting in similar positive impact on PFS in gliomas, just as PCV [27]; 3) a systematic review of 19 studies, including 2 randomized control trials and 1407 patients, demonstrating that RT/TMZ is at least as efficacious, and in many cases more efficacious, specifically in high-risk Grade II and III astrocytomas as compared to RT/PCV [28]; and 4) the lower toxicity profile and higher ease of administration of TMZ compared to PCV observed in these various trials.

Therefore, these high-risk Grade II and III astrocytomas (1p/19q intact, IDH wild-type, TERT promoter mutated) are increasingly being grouped with primary GBM and managed and treated as aggressively as molecular GBM, and new approved therapies that have shown to be effective against primary GBM (e.g. TMZ and TTFields) or novel experimental approaches designed to treat GBM should be tested in this high-risk group of diffuse astrocytomas.

